### 7.2 Interventions:

Study medication, to include 10-mg suvorexant and matching placebo, will be provided by Merck. The active medication will be suvorexant 10 mg every bedtime. The research pharmacist at EvergreenHealth will randomize the subject and the subject is provided active and placebo, in separate containers labeled for proper order of consumption based on study assignment. Study medication will be dispensed at randomization (Visit 2, start of Treatment Period 1) with separate pill bottles marked "Period 1, use this bottle first" and "Period 2, use this bottle after the break." An extra 6-day supply of medication will be provided for each study period to allow a window for scheduling of appointments.

Optional Drug Titration: There will be an optional titration to two pills at night (changes to suvorexant 20mg or matching placebo) after 5-7 days of each active treatment period. This will be based on a phone interview entailing answering questions about drug tolerance and whether the participant would like to escalate the dose of drug.

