Physical examination will be performed, both a general medical examination including vital signs and a neurological examination. Neurological exam will include disability rating by expanded disability status scale (EDSS) (Kurtzke 1983). Laboratory testing will include complete blood count (CBC), complete metabolic panel (CMP), with calculation of the Child-Pugh score for any subjects with liver dysfunction. Pre-menopausal women without surgical sterilization will have urine human chorionic gonadotropin (hCG) measured.

The wearable activity/sleep monitor will be dispensed at this visit to all subjects who meet eligibility criteria. This will be a FitBit™ device worn by the subjects throughout the remainder of the study. The research coordinator will oversee patient education around FitBit use. The FitBit is easy for subjects to put on and requires minimal user programming to upload data. Recorded outcomes are described below (see outcome measures). Subjects will be encouraged to wear the monitor 24-hours per day. Patients will be instructed to complete a sleep diary for seven days prior to next visit (see 11. Outcome measures).

## 10.3 Baseline Clinic Visit 2

Clinic Visit 2 will occur within 7-14 days after the screening visit. In addition to screening for eligibility, medications will be reviewed again to ensure stability of the MS medication regimen and absence of any prohibited medications.

Following confirmation of eligibility, an eligible patient will complete the baseline assessments of the insomnia severity index (ISI), modified fatigue impact scale (MFIS), Fatigue visual analogue scale (VAS-F), Global impression. The following measures will be provided for the participants to take home for use at the time of Phone Visit 2 and Phone Visit 5: Study scales (ISI, MFIS, VAS-F, BDI, Global impression). Sleep diaries will be provided for use after Phone Visit 1 and Phone Visit 3.

Following confirmation of eligibility, an eligible patient will be randomized in a 1:1 randomization scheme to receive suvorexant 10 mg qhs or placebo. Randomization will occur at the research pharmacy of EvergreenHealth using a computer-generated randomization list. The pharmacist will maintain a codebook indicating the treatment allocation of each subject. Study medication will be delivered by the research pharmacist to the research study staff from the

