### 10.5 Cross-over Phone Visit 2 (14 days post treatment)

Phone Visit 2 will occur at the completion of the first treatment period (day 14 following baseline). Medications will be reviewed again to ensure absence of any prohibited medications. Any possible adverse events (AE) will be assessed.

Study scales (ISI, MFIS, VAS-F, BDI, Global impression) will be self-administered by the participant with study staff oversight, as needed. Data from the wearable activity / sleep monitor will be collected. Completion of the 7-days sleep diary and scales (sQUAL and sFRESH) will be verified remotely.

Subjects will be instructed to take no study medication for one week, then to start taking the study medication (active or placebo) for Period 2.

### 10.6 Phone Visit 3 : Start of Treatment Period 2

Phone Visit 3 will occur 1 week after Phone Visit 2 (day 21 after baseline) and will mark the beginning of treatment period 2. Medications will be reviewed again to ensure stability of the MS medication regimen and absence of any prohibited medications. Any possible adverse events (AEs) will be assessed.

Subjects will be instructed to begin taking drug from the bottle marked "Period 2.". All subjects who received active medication in treatment period 1 will take placebo, and all subjects who received placebo in treatment period 1 will take active medication (10mg) while double blind.

## 10.7 Phone Visit 4

Phone Visit 4 will occur 5-7 days after Phone Visit 3 to review safety and tolerability through questioning about adverse events. BDI Q9 (suicidality risk) will be administered. Subjects with answer of 2 or 3 will be asked to discontinue study medication immediately and unscheduled visit or emergency referral will be arranged. Subjects with BDI Q9 score 0 or 1 who report no AEs on suvorexant 10 mg po QHS (or matched placebo) and who report a persistent sleep disturbance will be titrated to suvorexant 20 mg po QHS (or matched placebo) using a titration decision algorhythm. At this visit, subjects will be reminded to wear sleep monitors and to start recording sleep diaries.

### 10.8 Termination Phone Visit 5

Phone Visit 5 (final visit) will occur 2 weeks after Phone Visit 3 (day 35 after baseline). Medications will be reviewed again. Any possible AE will be assessed.

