#### **12.3 Serious Adverse Events**

A serious adverse event (SAE) is any AE that meets one of more of the following criteria:

- Is fatal or life-threatening
- Requires hospitalization or prolongs a current hospitalization
- Results in persistent or significant disability/incapacity
- Is a congenital anomaly
- Requires medical or surgical intervention to prevent one of the above outcomes

If any SAE occurs, the treatment status of the subject(s) may be revealed, as clinically indicated. If a patient discontinues medication use due to an AE, the event will be followed, when possible, until resolution. No interim analysis of safety data is planned because the entire study will be conducted over 2 months. However, the frequency of AEs will be under continuous scrutiny during the trial with comparison to AE rates that have been recorded in published PD drug trials.

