# 13. Data Management and Statistical Analysis

#### **Sample Size Considerations**

This is a prospective, double-blinded, randomized controlled pilot study. The purpose is to test a hypothesis in a preliminary fashion in this population with a specific neurological disease. In our initial statistical plan, the study was underpowered, based on an enrollment target of 30 subjects. We later increased the enrollment to 50 subjects to adequately power the study. We assume that no more than 10% of subjects will withdraw, be lost to follow-up or be dropped for protocol violations, leaving 45 subjects for final analysis. Power calculation is based on a cross-over design. We assume that the true difference in mean Insomnia Severity Index (ISI) between the treatments will be 1.75 units based on the findings of a cross-over trial by Herring et al for treatment effect of suvorexant on ISI in patients with primary insomnia. (Herring et al, 2012) We assume that our cohort with MS with adjustable dose titration (10mg and 20mg) will yield a slightly lower treatment response than that of the Herring cohort at 20mg (-2.0 units). We assume a normal distribution with standard deviation of the difference in the ISI is 4.1, based on normative data from Bastien, et al, who conducted the primary validation study. (Bastien et al, 2001) With these assumptions, the probability (power) is 81 percent that the study will detect a treatment difference at a two-sided 5.000 percent significance level. (PS Power and Sample Size Calculations, version 1.7.15, http://hedwig.mgh.harvard.edu/sample\_size/size.html#cross)

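### Section 12.3 compares adverse event rates with an undefined, unrelated class of trials and omits an interim safety analysis on the strength of a 2-month duration that fits one subject, not 50

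*Combined protocol and SAP*

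**What the plan says.** Section 12.3 (Serious Adverse Events) gives a single reason for having no interim look: "No interim analysis of safety data is planned because the entire study will be conducted over 2 months". It then keeps a running check, under which "the frequency of AEs will be under continuous scrutiny during the trial", and names the yardstick for that check: "comparison to AE rates that have been recorded in published PD drug trials". It gives no threshold, review interval or named reviewer.

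The timing of one subject's participation is set elsewhere. Section 10.3 says "Clinic Visit 2 will occur within 7-14 days after the screening visit". Section 10.8 says "Phone Visit 5 (final visit) will occur 2 weeks after Phone Visit 3 (day 35 after baseline". Section 7.2 adds slack: "An extra 6-day supply of medication will be provided for each study period to allow a window for scheduling of appointments". The Schedule of Events ends at Week 7-8.

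On trial size, the sample size section reports a rise from an initial target of 30: "We later increased the enrollment to 50 subjects to adequately power the study". Section 7.1 describes the trial as multi-center without giving the number of sites.

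**The concern.** An AE rate seen during a trial can be called high or low only against some reference. Here the investigator and all staff except the research pharmacist are blinded until the study is complete (end of Section 12.2). The rates they see therefore mix drug and placebo periods, and an external reference is their main means of judging them. The reference is also the only concrete element of the running check. If it describes another disease or drug class, the comparison tells the team nothing useful.

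The duration statement matters because it is the only argument offered for having no interim safety analysis. The argument has force if all exposure is over before an interim table could be prepared. It loses that force if subjects enter over many months, because events in early subjects could then inform the conduct of the trial for later ones.

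The protocol gives its own reasons for wanting a usable aggregate check. Section 5 says that people with MS may be more sensitive to the drug's adverse effects and that co-medication may add to daytime somnolence. What is at stake is mainly the recognition of an excess of common, non-serious events of that kind.

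**Working it through.** **The reference.** Set side by side:

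- Section 12.3 refers to PD drug trials.
- Section 4 (abbreviations) has no entry for PD, and the term appears nowhere else in the document.
- Section 6.1 defines the subject of the trial: suvorexant for insomnia in MS patients with fatigue.

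Whatever PD stands for, it names neither the disease, the condition nor the drug.

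**The duration.** The plan's figure is 2 months for the entire study. It cannot be reproduced as a whole-trial figure, because the documents give no accrual rate, accrual period or number of sites. What can be derived is one subject's course.

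Inputs: screening to baseline 7 to 14 days (Section 10.3); baseline to final visit 35 days, being 14 treatment + 7 washout + 14 treatment (Sections 7.1 and 10.8); spare supply 6 days per period (Section 7.2); 50 subjects (Sections 7.1 and 13).

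1. Course per subject = screening gap + 35.
   - Shortest: 7 + 35 = 42 days (6 weeks).
   - Longest: 14 + 35 = 49 days (7 weeks).
2. If the full scheduling slack is used in both periods, add 2 × 6 = 12 days: 42 + 12 = 54 to 49 + 12 = 61 days.
3. The Schedule of Events ends at Week 7-8, so at most 8 × 7 = 56 days. All three readings put a single subject's course at about 1.5 to 2 months.
4. Time left to screen everyone = study length − course per subject. I take 2 months as 61 days:
   - 61 − 42 = 19 days;
   - 61 − 49 = 12 days;
   - with full slack, 61 − 54 = 7 days down to 61 − 61 = 0 days.
   
   Taking 2 months as 60 or 62 days instead moves the 12-to-19-day window by one day either way.
5. Screening rate needed for 50 subjects: 50 / (19/7) = 18.4 per week, up to 50 / (12/7) = 29.2 per week. This assumes that no one fails screening.

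Section 10.1 describes a different pattern. Subjects are found as they come through clinical care, referrals and websites. Those from outside are offered telephone screening and asked to send records for review before a screening visit is booked.

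**Range for the true total.** These accrual rates are my assumptions, not the protocol's. Total months = 50 / rate + course, with the course 42/30.4 = 1.4 to 49/30.4 = 1.6 months.

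| Assumed accrual per month | Accrual (months) | Total (months) |
|---|---|---|
| 4 | 12.5 | 13.9 to 14.1 |
| 8 | 6.25 | 7.6 to 7.9 |
| 16 | 3.1 | 4.5 to 4.7 |

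Even at 16 per month the total is more than twice the stated 2 months. None of this enters the sample size, power or significance level.

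**The case against.** The strongest reply is that little depends on these two sentences. Section 12.3 forgoes a formal interim analysis, not safety review. AE frequency stays under continuous watch, and AEs are asked about at every contact from baseline on (Schedule of Events) and graded for severity and causality (Section 12.2). BDI question 9 is asked at Phone Visits 1 and 4 and the full BDI at Phone Visits 2 and 5, with a discontinuation rule attached (Sections 10.4, 10.7 and 12.1). Serious events have reporting timelines (Section 12.4) and allow unblinding (Section 12.3). No decision is tied to the external comparison. Omitting a formal interim analysis is also defensible in a 50-subject pilot with two 14-night periods, testing an approved drug within its approved dose range.

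Most of this stands, and it limits the point. A reader might infer that interim safety review has been abandoned, or that a run of suicidality events could pass unnoticed because of the PD wording. The documents support neither inference: the individual rules work whatever reference is named. A reader might also infer that PD is a known disease and the sentence was carried over from another protocol. That is possible, but it is only an inference, and the point does not need it.

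What the reply does not repair is the text itself. The individual safeguards do not compare AE frequency across subjects. The one provision that does so names an irrelevant reference, and the omission of an interim analysis rests on a duration the visit plan does not bear out. A sound decision can still carry an unsound reason.

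**Conclusion.** The concern holds as a correction to two operative sentences in Section 12.3. The AE reference is undefined and does not match the trial. The 2-month duration matches one subject's 42 to 49 days, and it could describe the whole trial only if all 50 subjects were screened within about 12 to 19 days. That result rests on the protocol's visit intervals and on taking 2 months as 61 days.

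The documents do not allow a statement of how long the trial would really take, so the amount of exposure that would accumulate without a scheduled aggregate look is unknown. Nor do they support saying that a formal interim analysis is required. The gap is confined to the aggregate AE comparison and the reason given for omitting the analysis. It should be corrected, and it does not undermine the design.

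**What to change.** 1. Replace the reference to PD trials with a relevant one, such as published suvorexant insomnia trials. Because blinded rates pool drug and placebo periods, say that they will be read against the reference's active and placebo rates taken together.
2. Replace the 2-month statement with the expected accrual period and the total trial duration. Giving only the per-subject duration would not be enough, since one subject's course is no reason to forgo a look at 50.
3. Either justify the absence of an interim analysis on other grounds (small pilot, short exposure, approved drug) or drop the duration argument. If it is dropped without another justification, have existing blinded staff tabulate pooled AE counts periodically against the named reference, and state who reviews the table and how often.

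Two additions may be tempting but are best left out. The trial's own placebo periods cannot serve blinded staff as a running comparator. A table by treatment kept by the research pharmacist would be a new unblinded procedure with nobody named to act on it.

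Cost: a few sentences of text and, if the tables are adopted, a few hours of tabulation. No new committee is needed, and sample size and power are unchanged.

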#### 12.4 Serious Adverse Events Reporting

The Food and Drug Administration (FDA) will be informed of SAEs as soon as possible or within 15 calendar days. In addition, the Investigator will notify the FDA of any unexpected fatal or life-threatening experience associated with the use of the drug as soon as possible, or within 7 calendar days, by telephone or facsimile. When the principal investigator has determined that an SAE requires reporting to the FDA (unexpected and possibly related to study drug), the following actions will be taken:

- Telephone the FDA immediately (day of awareness) in the case of reportable death or life-threatening events.
- Complete FDA Form 3500.
- Send the completed Form 3500 to the FDA (preferably by fax at [name]) within the timelines mentioned above.

Attach the photocopy of all examinations, medical notes and records related to the SAE and document the dates these were made. For laboratory results, include the laboratory normal ranges. For hospitalizations, Admission H&P, Discharge Summary, Consultative reports, etc. could be very helpful. In the case of a fatal event, provide an autopsy report, when it becomes available.

# 13. Data Management and Statistical Analysis

#### **Sample Size Considerations**

This is a prospective, double-blinded, randomized controlled pilot study. The purpose is to test a hypothesis in a preliminary fashion in this population with a specific neurological disease. In our initial statistical plan, the study was underpowered, based on an enrollment target of 30 subjects. We later increased the enrollment to 50 subjects to adequately power the study. We assume that no more than 10% of subjects will withdraw, be lost to follow-up or be dropped for protocol violations, leaving 45 subjects for final analysis. Power calculation is based on a cross-over design. We assume that the true difference in mean Insomnia Severity Index (ISI) between the treatments will be 1.75 units based on the findings of a cross-over trial by Herring et al for treatment effect of suvorexant on ISI in patients with primary insomnia. (Herring et al, 2012) We assume that our cohort with MS with adjustable dose titration (10mg and 20mg) will yield a slightly lower treatment response than that of the Herring cohort at 20mg (-2.0 units). We assume a normal distribution with standard deviation of the difference in the ISI is 4.1, based on normative data from Bastien, et al, who conducted the primary validation study. (Bastien et al, 2001) With these assumptions, the probability (power) is 81 percent that the study will detect a treatment difference at a two-sided 5.000 percent significance level. (PS Power and Sample Size Calculations, version 1.7.15, http://hedwig.mgh.harvard.edu/sample\_size/size.html#cross)

#### **Statistical Analysis**

Statistical analysis will be performed by a consulting statistician contracted with EvergreenHealth and whose services we have used on recent studies in MS. All data will remain blinded throughout the data analysis and will be un-blinded only in the event of a medical emergency.

Generally, the mean over the week prior to visit 2 (baseline) will be compared to the mean over the final week of Treatment Period 1 and the mean over the final week of Treatment Period 2 for treatment effects. This will be done by treatment arm. Level of significance will be p < 0.05. Minimum drug adherence for per-protocol criteria will be 75%. We plan to do both intention to treat and per-protocol analyses.

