Suvorexant may have other advantages that are of benefit specifically in the MS population. Suvorexant appears not to adversely affect next-day balance in healthy non-elderly subjects. In addition, suvorexant appears not to affect memory as measured by word recall. MS patients often have ataxia and cognitive impairment as a result of their disease. Orexins are considered to be involved in arousal and maintenance of the waking state. As such, suvorexant may provide unique clinical benefit as a treatment of MS fatigue with co-morbid insomnia.

This project proposes to study objective and clinical measures of insomnia, daytime sleepiness and fatigue in patients with MS fatigue and co-morbid insomnia while treated short-term with suvorexant 10-20mg versus placebo. Those qualifying will receive suvorexant and placebo for each of 14 nights in a cross over design with 7 nights of washout between treatments. There will be an optional titration to suvorexant 20mg (or matching placebo) after 5-7 days of each active treatment period. Primary outcome to be measured will be change in ISI on both conditions (Suvorexant 10/20mg versus placebo).

The primary outcome to be measured will be change from baseline for the two conditions (suvorexant 10/20 mg and placebo) on the Insomnia Severity Index.

Suvorexant is approved at doses up to 20 mg daily (Prescribing Information, Merck 2015). People with MS may be more sensitive to the therapeutic and adverse effects of suvorexant. It is also likely that subjects in a MS trial will be on other medications that may increase daytime somnolence. For these reasons, we are proposing a study of the 10-mg dose only. If suvorexant is found to be well-tolerated at a dose of 10 mg daily, future MS studies can explore the safety and efficacy of 20 mg daily.

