# 7. Methodology and Timeline

### 7.1 Methodology:

- Multi-center (Evergreen as principal site)
- N= 50. Confirmed MS diagnosis, age 18-75, inclusive.
- Double-blind, cross-over trial

- Four clinic visits: Screening, baseline, cross-over, termination
- Timeline:
  - 1) Screening
  - 2) Treatment 1 (baseline)
    - Subjects who meet eligibility criteria will be randomized to receive 2 weeks of treatment (treatment period 1) with either suvorexant 10 mg or matching placebo (1:1) with optional titration (see 7.2). Drug will be dispensed by the independent research pharmacist, keeping both study staff and the subject blinded. All subjects, whether in placebo or active arm, will receive a wearable sleep monitor to be worn continuously throughout the study. The subjects will be allowed to keep the wearable sleep monitor in addition to a small monetary reimbursement per visit.
  - o 3) Washout (14 days post baseline)
    - At the end of treatment period 1 (2 weeks), subjects will undergo efficacy assessment with repeated clinical scales. Subjects will then go through a 1week open-label off-drug washout period. Subjects will then be crossed over into the alternate treatment group, which will once again be doubleblinded; those on active treatment for period 1 will be switched to placebo, and those on placebo in period 1 will be switched to active treatment.
  - 4) Treatment 2 (7 days post washout, 21 days post baseline)
    - Treatment period 2 will also be 2 weeks long, with crossover from Period 1 either suvorexant 10mg or matching placebo, with optional titration (see 7.2). At the end of this, subjects will undergo final assessment with clinical scales.

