# 11. Outcome Measures

All outcome measures will be based on end of treatment period compared to baseline visit.

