#### • Change in Modified Fatigue Index Scale (MFIS) Score at 2 weeks vs baseline.

The MFIS is a well-validated fatigue measure in MS (Tellez et al. 2005). The MFIS has a Cronbach's alpha of 0.81 (National MS Society). In MS, it has been found to have intratest reliability, no ceiling or floor effects and greater sensitivity to change than the FSS (Kos et al. 2003). The test has 21 items with physical, cognitive and psychosocial subscales. Subjects will complete the MFIS as the first test conducted on the day of visit. Their ratings on the 21-item questionnaire will be based on their fatigue experience over the previous 1 week. The total MFIS score will be used for primary efficacy measure.

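### The analysis section writes only comparisons with baseline and does not name the within-subject suvorexant-versus-placebo test that the trial is powered for

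*Combined protocol and SAP*

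**What the plan says.** Two places in the plan fix the intended contrast. Section 5 gives it as "Primary outcome to be measured will be change in ISI on both conditions (Suvorexant 10/20mg versus placebo"), and then restates the outcome as "change from baseline for the two conditions (suvorexant 10/20 mg and placebo) on the Insomnia Severity Index". The sample-size text in section 13 assumes a cross-over design, a 1.75-unit ISI difference between the treatments, an SD of the difference of 4.1, 45 analysed subjects out of 50, and 81% power at a two-sided 5% level.

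The Statistical Analysis text, also in section 13, is the only place that describes how efficacy will be analysed. Its rule begins "Generally, the mean over the week prior to visit 2 (baseline) will be compared to the mean over the final week". The same comparison is then written for each of the two periods in turn, and the rule closes with "the mean over the final week of Treatment Period 2 for treatment effects. This will be done by treatment arm". It then sets the significance level and a 75% adherence threshold, and adds "We plan to do both intention to treat and per-protocol analyses".

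Section 11 uses the same reference point: "All outcome measures will be based on end of treatment period compared to baseline visit". Within section 11.2, the fatigue scale is listed as "Change in Modified Fatigue Index Scale (MFIS) Score at 2 weeks vs baseline", and the wearable measures set a screening-period average against the last seven nights of each treatment period.

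**The concern.** The plan powers one comparison and writes down another. No section states a suvorexant-minus-placebo test, a paired or cross-over analysis, or a period term. The comparison that is written has baseline as its reference.

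A change from baseline on suvorexant contains everything that also happens on placebo: placebo response, regression to the mean in subjects selected for insomnia, and time. Only the contrast with placebo removes these. If the analysis section is followed as it stands, the reported tests do not use the placebo control and are not the test that the 81% describes. Even if the contrast is inferred, its form is open: paired test or model, with or without a period term, complete pairs or all subjects.

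A smaller mismatch points the same way. A mean over the final week suits the diary and the wearable. The ISI is completed once at baseline and once at the end of each period (Schedule of Events and sections 10.3, 10.5 and 10.8), so there is no weekly mean to take.

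**Working it through.** **1. Reproduce the plan's power.** Inputs from the sample-size text: difference 1.75, SD of the difference 4.1, n = 45 (50 × 0.9), two-sided 0.05.

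- Standard error: 4.1 / √45 = 0.611. Standardised difference: 1.75 / 0.611 = 2.863.
- Normal approximation: Φ(2.863 − 1.960) = Φ(0.903) = 81.7%.
- Noncentral t, paired, 44 df: 80.0%.
- Noncentral t with a period term, sequences of 22 and 23, 43 df: 79.9%.

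The stated 81% is reproduced. Its inputs are a difference between treatments and the SD of that difference, so it describes the within-subject drug-placebo contrast. A before-after test would need a change from baseline and the SD of that change, and the documents give neither.

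**2. Set the intended contrast beside the written one.**

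| Place | Comparison |
|---|---|
| Section 5 | suvorexant versus placebo, change in ISI |
| Section 13, sample size | suvorexant versus placebo, cross-over difference |
| Section 13, Statistical Analysis | baseline week versus final week of each period, by arm |
| Section 11, opening line | end of period versus baseline |
| Section 11.2, fatigue scale and wearable | two weeks, or final seven nights, versus baseline |

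**3. What arm means.** Section 7.1 has "whether in placebo or active arm", which points to drug or placebo. Section 10.3 keeps staff blinded to the treatment arm assigned at randomisation, which in a cross-over could mean sequence. On the first meaning, the rule is a before-after comparison within each condition. On the second, it is a before-after layout by period within each sequence. Neither states the drug-placebo test.

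**4. Relation to change from baseline.** There is one baseline, so for a subject with both periods (S − B) − (P − B) = S − P. The primary outcome in section 5 and the powered difference are then the same quantity, and naming the contrast does not alter the outcome.

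**5. Illustration of the literal reading.** Assumed, not in the documents: n = 45, no drug effect, the same mean fall in both conditions, SD of change 4.1, correlation of the two changes 0.5, paired t tests against baseline. A mean fall of t(0.975, 44) × 4.1 / √45 = 2.015 × 0.611 = 1.23 points is significant against baseline.

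| Shared fall (points) | Suvorexant significant vs baseline | Suvorexant significant, placebo not | Direct suvorexant-placebo test |
|---|---|---|---|
| 1 | 36% | 16% | about 5% |
| 2 | 89% | 7% | about 5% |
| 3 | 99.8% | 0.2% | about 5% |

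The second column comes from the noncentral t distribution and the last two from simulation. With SD of change from 3 to 6 and correlation from 0.3 to 0.7, the third column ranges over about 9% to 20%, under 1% to 20%, and 0% to 8% at falls of 1, 2 and 3 points.

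**The case against.** The strongest reply is that the contrast is already fixed. Section 5 names suvorexant versus placebo, and the sample-size text gives the endpoint, the design, the SD of the difference and a two-sided level. The analysis rule opens with a hedge, says it serves treatment effects, and never says that each condition is tested separately against baseline. Tabulating baseline and both periods by sequence is an ordinary cross-over layout. All of this stands. A reader might infer that the trial has abandoned its placebo control; the documents do not support that. What is missing is the test, and no reading of arm supplies it.

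A reader might also take the 36% / 89% / 99.8% column as the trial's false-positive rate. The documents do not support that either. The SD of change and the shared fall are assumed, and placebo would be tested in the same way, so a large shared fall usually makes both conditions significant and visibly fails to separate them. The misleading pattern is suvorexant significant and placebo not. It is much less frequent, though it can exceed 5%.

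The ISI wording is a minor point. With one-week recall, the single end-of-period score already covers the final week.

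The plan calls itself a pilot with a preliminary hypothesis. But the same paragraph raises enrolment from 30 to 50 so that power is adequate and claims 81% at a two-sided level. That claim needs a named test.

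**Conclusion.** The point holds as a gap between the intended primary contrast and the written analysis. The contrast can be inferred from section 5 and the sample-size text, but its test is not stated anywhere, and the only comparison that is stated does not use the placebo control. This conclusion rests on the text alone and needs no assumed figure.

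No number in the plan is in dispute: the 81% stands (79.9% to 81.7% depending on method). The illustrative rates depend on assumed inputs and only show why a before-after result cannot stand in for the direct contrast. Because the gap concerns the primary test of a placebo-controlled trial, it should be closed before unblinding.

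**What to change.** In the Statistical Analysis text of section 13:

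- Keep the baseline-week and final-week definitions for the diary and wearable measures.
- State that the ISI and the other scales use the single baseline score and the single end-of-period score.
- Replace the sentence that organises the comparison by treatment arm with:

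> For the ISI (primary) and each secondary outcome measured in both periods, the treatment effect is the within-subject suvorexant-minus-placebo difference in change from baseline, tested two-sided at 0.05 in a two-period crossover analysis that includes a period term (for example a mixed model with treatment, period and sequence as fixed effects and subject as a random effect). Comparisons with baseline within a condition are descriptive.

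Add the same contrast to the opening line of section 11.

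The named contrast is the essential change. The model form is a suggestion, since a paired test has practically the same power (80.0% against 79.9% with a period term). The sponsor should say which is used, because the choice also decides whether subjects with only one period contribute.

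The cost is wording in two places. There are no new data and no more patients, and the sample size, alpha, the stated 81%, both analysis sets and the 75% adherence criterion do not change.
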